The survey will have four sample components. The Primary Sample will consist of 5,000 households within 2,717 baris, that is, clusters of households related by blood or marriage. This sample will cover 33 percent of the total number of baris in the Matlab surveillance area. A second sample will consist of a follow-up of 900 households of women who participated in the Determinants of Natural Fertility Study (DNFS) and for whom detailed retrospective family planning and pregnancy history data already exist. An Outmigrant Sample will consist of the households of 300 female and 300 male outmigrants who left households in the Primary Sample between 1982 and the date of the MHSS and have not returned. This sample represents about 10 percent of all outmigrants

(Continued)

from the area since 1982. Finally, a Community Sample will yield information on community infrastructure and services and detailed data on 500 health/family planning providers, and health, family planning, and education facilities potentially serving the households in the Primary Sample.

Within each household, all members aged 50 and over will be included; in the 15-49 age group, the household head and the head's spouse and one randomly chosen adult; and in the 0-14 age category, only children belonging to the adult respondents will be eligible for selection and only one of these children will be chosen.

CRITIQUE: The proposed survey is expected to build upon existing data collected from the Matlab area, resulting in a very rich set of panel data for use in the analysis of adult health, health care utilization, and transfer networks. It will be a major effort designed to fill in the gaps in information about socioeconomic background, adult health, and health care utilization from the previous surveys. A very useful aspect of the design of the survey is that previous information on, say, migration and pregnancies will be printed prior to the MHSS and will be used by interviewers to prompt respondents in their recall. This is expected to aid recall, reducing the time needed for responses and enhancing accuracy, and presumably also facilitating the linking of the existing databases with the new survey data. Moreover, this prior work with existing databases could be used to identify weaknesses and existing information and point to areas where redundancies in data collection should be built into the MHSS.

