- o The wide variety of health status measures mentioned above in addition to the anthropometric data and estimates of time to sterility on females allows us to examine a greater range of women's health and nutrition outcomes than has been possible in earlier studies.
- o Our access to prior measures of health and nutritional status for a subsample of women (described in detail in the sampling section) allows us to control for past health status, an important and rarely available determinant of current health status.
- o The comprehensive information on pregnancy/lactation histories will help characterize the impact of pregnancy related processes on later health more precisely than has been possible in other studies. This is particularly true for 1/2 the primary sample for whom we have prospective data on pregnancy/lactation/morbidity since 1978--(see Summary Research Plan, Tables 2, 3).
- o The detailed information on economic status of women and their families in this survey helps us control for socio-economic factors more completely than was possible in earlier studies of this issue.
- o The presence of externally induced variation in family planning services in Matlab (through the institution of the family planning intervention project in 1978) provides a rare opportunity to examine program effects on health and demographic outcomes without having to worry about the potential selectivity of program placement.

Project 4—Human Capital, Migration and Inter-generational Transfers. Project 4 uses the extensive information that will be collected on child anthropometrics, cognitive achievement and educational attainment to examine inter-generational investments in health and education. The detailed data available on household structure also allows us to examine the impact of living arrangements on investments in health and education. Data of this type have not been available before. In addition the availability of extensive community level information on family planning, maternal and child health services allows us to control for community effects much more precisely than has been attempted prior to this analysis.

In addition to the above, the MHSS data will allow analysts to investigate other research topics concerned with family decision-making in developing countries, with particular relevance to the elderly.

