- * As noted above, within the bari we will select up to two households. For baris with two or fewer households, all households will be chosen. For baris with greater than two households, the first household will be chosen at random; the second household will be selected from the bari in order of preference as follows: (i) The household of the father and/or mother of the head of the first sampled household (ii) A randomly chosen household containing a brother of the head of the first sampled household (iii) A randomly chosen household containing a son of the head of the first sampled household (iv) A second randomly selected household.
- * Once the two households in the bari are selected, respondents within each household will be chosen in three age strata. (i) All household members 50 years and above will be chosen as respondents. (ii) From the pool of household members aged 15-49, if there are two or less we will pick all. If there are more

than two, the following strategy will be employed: If an individual is the household head or the wife of an household head, then that individual will always be chosen. In addition to the household head and or spouse, another individual 15-49 will be chosen at random along with their spouse if present. At this stage if we have two 15-49 year old respondents we will stop. However if we have only one respondent in the 15-49 age group and there are other 15-49 year old individuals in the household, we will pick another at random along with their spouse if present. (This will lead to a maximum of 4 adult respondents in the 15-49 age group); (iii) Among the pool of children in the household aged 0-14 years, all those sharing a parent will be pooled together in the same sibling group. Only sibling groups whose parent has been selected in rounds 1 or 2 above are eligible for selection as child respondents. From those eligible, one sibling group will be chosen at random and from within that group upto two siblings will be chosen. If that group has only one child, then another sibling group from the eligible pool will be chosen. Here again upto two siblings will be chosen. (This will lead to a maximum of 3 child respondents aged 0-14 years).

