The development of weights for sub-bari data elements: The proposed primary sampling units are the bari's. Sampling proportional to number of bari's within the two family planning regions (treatment and comparison) produces a self weighting sample for bari level analysis. As we consider the sampling stages within the bari the weights get a bit more complicated. The first stage of within bari sampling is the selection of households. The second stage is the selection of adults within households. The third stage is the selection of children of the adults. The calculation of sampling probabilities is facilitated by the detailed Matlab household rosters.

The probability of selecting a particular household is the sum of the probabilities of selecting the household first and second. For example, in bari's with more than two households every household has a probability of $1/(\text{number of households})$ of being selected first. The probability of a household being selected second is a more complicated. It is a function of the relationships between the households and the sampling rules. For example, if you are the father of the first sampled household's head you are sampled with conditional probability one given the first household was sampled. However, you could also be sampled second if another household is sampled first by the same or a different sampling rule. All of the probabilities of the ways you could be sampled second must be added up and then added to the probability that you are sampled first to get your household's overall sampling probability. Although a bit complicated these probabilities can be calculated from the bari rosters. In summary, the probability of selecting any given household is $p(\text{selecting the bari}) * p(\text{selecting the household given the bari is selected})$. Weights for household level analysis are proportional to the reciprocal of this probability.

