The probability of selecting a particular adult given that their household was selected is a similar calculation to the household sampling probability calculation. We need to enumerate all of the ways that a particular adult could be sampled. These are either through sampling with certainty, random sampling from a stratum, or through the kinship rules. The overall probability that a household will be selected can then be calculated from the conditional probabilities of the various ways that the household could be sampled. In summary, the probability of selecting any given adult is $p(\text{selecting the bari}) * p(\text{selecting the household given the bari is selected}) * p(\text{probability of selecting the adult given that the household is selected})$. Weights for individual adult level analysis are proportional to the reciprocal of this probability.

Sampling probabilities for the children is a similar calculation to the adult calculation although a bit simpler due to the simpler sampling rules. Given the selection of a sibling group, the probability that a particular child is chosen is inversely proportional the number of siblings in the group. The only complication is the possibility that a child is sampled in a second stage because the first sibling group only had one child. These probabilities can be calculated from information on the roster. In summary, the probability of selecting any given child is $p(\text{selecting the bari}) * p(\text{selecting the household given the bari is selected}) * p(\text{probability of selecting the adult given that the household is selected}) * p(\text{selecting the child given that the child's adult was selected})$. Weights for individual child level analysis are proportional to the reciprocal of this probability.

Every member of the bari has a well described and non-zero probability of being sampled. The probabilities are a bit difficult to work out due to the importance of the family structures and interconnections. This is, however, an unavoidable consequence of the importance of collecting data that will inform the effects of family relationships on the outcomes of interest.

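### The protocol says every bari member can be sampled, but a child aged 0-14 with no selectable parent in the household has selection probability zero

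*Protocol*

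**What the plan says.** The rule is in section D, Sample Design, in the steps for choosing respondents within a household. Round 1 covers older members: "All household members 50 years and above will be chosen as respondents". Round 2 selects members aged 15-49. Round 3 covers children. It first forms groups: "Among the pool of children in the household aged 0-14 years, all those sharing a parent will be pooled together in the same sibling group". It then restricts them: "Only sibling groups whose parent has been selected in rounds 1 or 2 above are eligible for selection as child respondents". At most three children are taken.

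The same limit appears in two other places. The weights paragraph in Properties of Sample Design describes the last step as "The third stage is the selection of children of the adults". The review panel's description at the front of the protocol says that "only children belonging to the adult respondents will be eligible for selection".

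The weights paragraphs write the child probability as a product of four factors: bari, household given bari, adult given household, and child given that the child's adult was selected. They add: "Weights for individual child level analysis are proportional to the reciprocal of this probability". They close with the general claim: "Every member of the bari has a well described and non-zero probability of being sampled".

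The description of Project 4 in section B relies on child anthropometrics, cognitive achievement and schooling, and says: "The detailed data available on household structure also allows us to examine the impact of living arrangements on investments in health and education".

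**The concern.** A probability sample supports weighted inference to a population only if every member has a positive chance of selection. The protocol asserts this property for the whole bari, while its own rule denies it to one group of children: those for whom no parent is among the household members who can be selected. They may live with grandparents, other kin or a guardian, but selecting that adult does not make the child eligible.

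Three things are at stake. First, direct child measurements would describe children living with a parent, while the documentation says coverage is complete. The data are meant for public release, so outside users would rely on that statement. Second, living without a parent is one of the contrasts that a study of living arrangements might want, and no measured outcome would be available for it. Third, the gap cannot be repaired later: respondents are fixed from the rosters before fieldwork, and children who were never sampled do not show up as non-response. The same within-household scheme is used for the DNFS and outmigrant samples, so the gap carries over to them.

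**Working it through.** No power or sample-size figure underlies the claim. The check is whether the selection rules deliver the stated property.

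**Step 1. Rule against claim.** Under the protocol's formula, p(child) = p(bari) x p(household | bari) x p(adult | household) x p(child | adult selected). If no parent lives in the household, there is no adult to enter the third factor and the child belongs to no eligible group. So p(child) = 0, and the weight 1/p is undefined. No other section gives a second route. The references to caregivers, a best guardian and consent by guardians settle who answers or consents for a child, not which child is eligible.

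**Step 2. Test household.** Take a selected household with a head aged 55, wife 50, son 28, son's wife 24 and an unmarried adult 20. Its children are one child of the head, three of the son, one with both parents dead and one whose parents live elsewhere.

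- Round 1: head and wife are taken with certainty.
- Round 2: the pool is the son, his wife and the unmarried adult. With probability 2/3 the first pick is one of the couple; both enter and selection stops. With probability 1/3 it is the unmarried adult, and the second pick brings in the couple. The couple therefore has probability 1 and the unmarried adult 1/3.
- Round 3: two groups are eligible. With probability 1/2 the head's only child comes first, followed by two of the son's three. With probability 1/2 two of the son's three come first and selection stops.

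| Member | Probability given household |
|---|---|
| Head, wife, son, son's wife | 1.00 each |
| Unmarried adult | 0.33 |
| Child of the head | 0.50 |
| Each child of the son | 0.67 |
| Child with both parents dead | 0.00 |
| Child with parents elsewhere | 0.00 |

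A simulation of 200,000 draws gave the same values. Households and adults do have positive probability: in larger baris each household can be drawn first with probability 1/(number of households). The claim fails only for children.

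**Step 3. Size.** The planned number of child respondents is 3,849 + 3,614 = 7,463 (Tables 2 and 3). These are children selected under the rule. If a share s of all children 0-14 is excluded, and they would otherwise have been drawn at the same rate, the number left out is s/(1 - s) x 7,463. The documents do not give s, so these values are assumptions:

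- s = 2%: 0.02/0.98 x 7,463 = 152
- s = 6%: 0.06/0.94 x 7,463 = 476

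Bias in an overall child mean is s x d, where d is the difference from other children in SD units, also assumed:

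- s = 1%, d = 0.25: 0.0025 SD
- s = 5%, d = 0.5: 0.025 SD
- s = 10%, d = 0.5: 0.05 SD

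**The case against.** The best defence is that the restriction is deliberate and openly stated. Sample Design explains that parent-child pairs are wanted for studying resource pooling and family heterogeneity, and the survey's main focus is adults and the elderly. On that view only one sentence is too broad. This is fair as far as it goes: the restriction is a legitimate choice. The sentence is still wrong, and no section narrows the child population to match.

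A reader might infer more than the documents support.

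- *That these children vanish from all child data, so that fostered and parent-resident children cannot be compared at all.* Not so. The section on characteristics of children has parents report on their ever-born children wherever they live, with morbidity and health care use for living children aged 0-14. Some fostered children therefore enter, including through parents in the outmigrant sample. The bari and household modules record age, sex and education for all members, so schooling can be compared. What is missing is direct measurement, and most information on children with both parents dead.
- *That all orphans are excluded.* A child living with one surviving parent stays eligible unless that parent is under 15.
- *That the plan foresaw such children because it mentions caregivers and guardians.* The best-guardian wording arises where a male respondent has no spouse present, so a father is in the household. It is weak evidence.
- *That Project 4 fails.* Its description names living arrangements in general, not fostering or orphanhood, and its full proposal is not shown here.

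Reading the parent rule across both sampled households could admit a child fostered within the bari. The plain reading is within each household, and children whose parents are dead or outside the bari stay at zero either way.

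**Conclusion.** The coverage statement is false as written. This follows from the protocol's own rules and needs no outside figure. Children aged 0-14 with no parent among the household's selectable members have probability zero, and weighting cannot bring them back. The loss is complete for that group in anthropometrics, cognitive tests and weighted child-level analyses, and partial or absent elsewhere.

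The documents do not show that the effect on overall child results is large. The count and bias above rest entirely on assumed shares and differences, and across the range tried the bias never exceeds 0.05 SD. In a treatment-against-comparison contrast it would largely cancel if the share and the difference were similar in the two areas, since one rule applies to both. The point is therefore a needed correction of a stated design property and of the child target population. It is not a flaw that undermines the survey's main aims.

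**What to change.** **Preferred, before the draw.** In round 3 of Sample Design, also make a sibling group eligible when none of its parents lives in the household, with the head or main caregiver as proxy. Keep the cap of three children. In Properties of Sample Design, add this route to the child probability; the adult factor does not apply to these children. Recompute the probability of the other children in the same households, because they now compete with more groups.

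**Cost.** The draw already runs from household rosters, so the programming change is small.

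- Households whose only children have no parent present now yield no child respondent and would yield some, so there are a few extra measurements.
- Elsewhere some parent-child pairs are displaced. In the test household, with four eligible groups instead of two, each single-child group has probability 1/4 + (2/4 x 1/3) = 0.42. The son's group has 1/4 + (3/4 x 1/3) = 0.50, so each of his children has 0.50 x 2/3 = 0.33. The head's child falls from 0.50 to 0.42 and each of the son's from 0.67 to 0.33. That household was built with two parentless children, so typical displacement would be smaller.
- The child counts in Tables 2 and 3 change slightly.

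**Minimum.** Leave the rule alone, limit the coverage statement to the members for whom it is true, define the child target population as children living with a parent, and carry that definition into the user documentation. The rosters can supply the share excluded, which would replace the assumed range above.

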- o an anthropometric module which will measure anthropometrics for all household respondents;
- o a cognitive testing module which will administer tests of general cognitive ability and culture specific verbal and mathematical achievement to all household respondents

- o a physical activity and dietary module which will collect information on average weekly physical activity and 24 hr dietary recall for all female household respondents aged 15-49 years;

SAMPLE DESIGN

Overview: The Matlab Surveillance area has a total population of approximately 192,000 individuals in 149 villages, encompassing an area which is 18 miles wide and 11 miles long, about 45 miles south east of Dhaka the capital of Bangladesh. Since the late 1960s, ICDDR,B has operated a demographic surveillance system (DSS) in this area. Linked computerized records however are available from 1974 on. ICDDR assigned blocks of contiguous villages in the DSS area to be in either a (i) comparison area, which receives government family planning and health services; or (ii) a treatment area, which, since 1978, has had family planning interventions and, since 1982, expanded maternal and child health service. The treatment and comparison areas are comparable in size, with roughly 96,000 individuals in each. In addition to the regular population surveillance in both areas, additional data have been collected on contraceptive use and continuation, pregnancy status as assessed by presence of menstruation, and lactation status for all women ages 15 to 49 in the treatment area only.

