The compact nature of Matlab makes a simple sampling design practical and efficient. The small geographical area, compared to more dispersed study regions, removes the need for any kind of multiple stage cluster sampling. The **primary sample** of the MHSS (as opposed to the other three components of the MHSS, the DNFS followup sample, the Outmigrant sample and the Community sample) will consist of a probability sample of 2717 baris in the Matlab surveillance area in both the treatment and comparison areas. The bari is the basic unit of social organization in rural Bangladesh and in Matlab in particular. Baris usually consist of a cluster of households linked in many instances in a kin network-(note however that about 16% of baris consist only of a single household and even in multi-household baris, kin networks may exist only for sub-clusters of households). Sampling baris rather than households provides a better representation of family networks, a major focus of the program project, and gives us the opportunity to collect data on common bari resources. Within each bari, we will select upto two households for detailed interviews and within households we will interview selected respondents.

Key features in the proposed sample design for the **primary sample** are as follows:

- o The sampling design will be a stratified random sample with the bari as the primary sampling unit (PSU). The allocation of sample size to strata will be proportional to the number of baris in the strata. The Matlab region will be divided into two roughly equal strata (in terms of households and baris): (1) Matlab treatment area; (2) Matlab comparison area. For bari level analyses the sample will be self-weighting.
The sample of baris will be drawn from the DSS 1994 sample frame. Baris will be randomly sampled from the treatment and comparison frame. In each bari we will obtain information on bari-level characteristics from a knowledgeable member or members of the bari (we recognize the possibility that there may be subclusters of households within the bari, and we may need the help of more than one individual to get the core bari information).
In addition to getting bari level information, we will sample up to two households in each bari. The net (interviewed) sample will thus consist of 2717 baris and 5000 households.

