Endogeneity issues in household formation: We recognize the important but difficult issues surrounding the endogeneity of bari or household level variables due to bari and household formation decisions (or perhaps more accurately the decision not to subdivide). For example the use of bari size as an explanatory variable in an analysis of health outcomes is troublesome because some elements of the bari have decided to stay or leave. There is no universal solution to this problem from the sampling tradition. For some purposes re-weighting the sample to reflect the outmigration from the bari may be useful. This can be done in the fashion of traditional non-response adjustments in survey sampling. But we must recognize that this kind of adjustment assumes an exchangeability between those that left and those that stayed. Clearly this is a bad assumption for many analyses. For some analyses there may be no need to adjust beyond recognizing that the sampling frame is a current snapshot. This is appropriate for analyses where the endogeneity can be addressed by treating the endogenous variables as endogenous but predetermined.

Ultimately the issue of endogeneity must be addressed as a modeling issue rather than a sampling issue. The non-response adjustment can be thought of as a very crude selection model. Clearly more sophisticated selection models are needed for many questions. Likewise real endogeneity in analyses where the endogenous variables can not be treated as predetermined requires careful modeling. Support of these modeling efforts are an important part of sample design. In particular the collection of information about outmigrants is useful. In addition items that may help identify selection equations (e.g. wages in other areas, distance to alternative locations) must be collected.

Power of the sample design: The simplest level at which to examine the power of this design is for bari level analyses. There are no clustering or design effects for analyses at this level. It is, however, the level at which we have the smallest sample size. This makes bari level power calculations useful "worst case" calculations.

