We will consider the power of the primary sample alone. The power with the DNFS/outmigrant sample incorporated will be even larger when such an incorporation is appropriate. From our experience with the IRMS, we have selected an outcome measure to explore the power of this design, general health status (GHS). For adults in IRMS GHS had a mean of 1.9 and a standard deviation of .64. If we wish to detect a difference in GHS for two groups that split the population roughly equally, for example treatment area vs comparison area, the power to detect a difference of .05 (or less than 1/12 of a standard deviation) is 38%. At a difference of .1 (or less than 1/6 of a standard deviation) the power is up to 96%. The effective sample size for other levels of analyses are larger but must be adjusted for design effects. For example, the sample will have almost twice as many households as baris. However with a large clustering effect ($\rho = .25$) the effective sample size would be only 60% larger. Never-the-less the power would still be larger than the already substantial bari level power. Multivariate modeling will typically reduce the clustering by the inclusion of explanatory variables resulting in even larger effective sample sizes.

SURVEY INSTRUMENTS

Bari and Household Questionnaires

Table 3 summarizes the modules of the questionnaire to be administered at the bari, household and individual levels. In the subsequent paragraphs we describe in detail the content of the different modules of the questionnaire.

	Sample baris	Sampl ehhs	0-14	15-49 Male	15-49 Female	50+ Mal e	50+ Female
Expected # of respondents	2717	5000	7463	4388	4779	2840	2328
Control Card	X	X					
Bari Module	X						
Household Module		X					
Health & Physical Performance				X	X	X	X
Life History-(mstat,educ,work, inc,mig,nres-kin)				X	X	X	X
Fertility					X		X
Child Characteristics					X		X
Anthropometrics			X	X	X	X	X
Cognitive Ability			X	X	X	X	X
Physical Activity & Diet					X		

****Note:** In addition to the primary sample above, 900 households will be interviewed as part of the DNFS sample and 600 households as part of the Outmigrant sample. In both the DNFS outmigrant samples, the same within household selection procedure will be followed, with the caveat that the DNFS woman and the outmigrant individual will always be selected. The bari questionnaires will be administered only where applicable (i.e. in rural areas).

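### The 38%/96% power is not a worst case for treatment versus comparison area, because area was assigned by blocks of contiguous villages

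*Protocol*

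**What the plan says.** Section D, under Properties of Sample Design, discusses power at the bari level. It states that "There are no clustering or design effects for analyses at this level" and adds: "It is, however, the level at which we have the smallest sample size". From this it concludes that the bari-level figures serve as a worst case.

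The calculation takes its outcome from an earlier survey: "For adults in IRMS GHS had a mean of 1.9 and a standard deviation of .64". The comparison is "for two groups that split the population roughly equally, for example treatment area vs comparison area". It reports that "the power to detect a difference of .05 (or less than 1/12 of a standard deviation) is 38" per cent, and that power for a difference of .1 is 96%. The sample size is given under Sample Design: "The net (interviewed) sample will thus consist of 2717 baris and 5000 households". No significance level is stated. The only clustering considered is that of households within a bari (rho .25).

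The Overview of the Sample Design says how the two areas arose: "ICDDR assigned blocks of contiguous villages in the DSS area to be in either a (i) comparison area" or a treatment area. It gives 149 villages but no number of blocks.

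**The concern.** Baris in one block share both the programme assignment and the local environment. The Community Questionnaire section itself reports considerable variation between villages in community characteristics. When exposure is assigned to blocks of villages, the variance between villages and between blocks belongs in the standard error of the exposure contrast, however the baris were drawn. A calculation with independent baris leaves it out.

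This contrast is prominent. Specific Aims and Background both present the area assignment as an exogenous experiment for estimating programme effects, and the impact of community services is a stated aim. If the power shown is taken as a floor, readers will think the survey better able to detect programme effects than the document can support.

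**Working it through.** **1. The stated figures.** Inputs: 2717 baris, split 1:1 (1358.5 per area); SD .64; differences .05 and .1.

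- SE = .64 × √(2/1358.5) = .02456, so z = .05/.02456 = 2.04 and .1/.02456 = 4.07.
- One-sided 1% (critical value 2.326): Φ(2.036 − 2.326) = 38.6% and Φ(4.072 − 2.326) = 96.0%. Both stated figures are reproduced.
- Two-sided 5%: 53% and 98%. These do not match.

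The figures therefore come from 2717 independent units with a design effect of exactly 1, apparently at one-sided 1% (equivalently two-sided 2%).

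**2. The SD.** The value .64 describes individual adults, yet it is applied to one value per bari. Table 3 expects 4388 + 4779 + 2840 + 2328 = 14,335 adults, or 14,335/2717 = 5.28 per bari. Assume that the protocol's rho of .25 also applies to adults within a bari. The SD of a bari mean is then .64 × √[(1 + 4.28 × .25)/5.28] = about .40. On this point the stated calculation is conservative.

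**3. Village clustering with all adults used.** Adults per village: 14,335/149 = 96.2. The design effect is 1 + (5.28 − 1) × .25 + (96.2 − 5.28) × ICC. The ICCs are assumptions.

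| Village ICC | Design effect | Effective n | Power for .05 / .1, one-sided 1% |
|---|---|---|---|
| .01 | 2.98 | 4,813 | 65% / 99.9% |
| .02 | 3.89 | 3,687 | 52% / 99.2% |
| .05 | 6.62 | 2,167 | 31% / 90.5% |

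Effective n equals 2717 when 2.07 + 90.9 × ICC = 5.28, that is, at an ICC of about .035. Below that value, village clustering alone does not bring power under 38%/96%.

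**4. Block clustering with all adults used.** The number of blocks B and the ICC are both assumptions. The design effect is 1 + (5.28 − 1) × .25 + (14,335/B − 5.28) × .005. SE = .64 × √(4/effective n), and power comes from the noncentral t on B − 2 degrees of freedom, two-sided 5%.

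| Blocks | Design effect | Effective n | SE | .1/SE | Critical t | Power for .1 |
|---|---|---|---|---|---|---|
| 6 | 13.99 | 1,025 | .0400 | 2.50 | 2.78 | 48% |
| 8 | 11.00 | 1,303 | .0355 | 2.82 | 2.45 | 65% |
| 12 | 8.02 | 1,788 | .0303 | 3.30 | 2.23 | 84% |

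At a block ICC of .01 the same steps give 29%, 42% and 62%. The independent-bari figure at this significance level is 98%.

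**The case against.** The best defence is that the quoted sentence is true where it stands. It belongs to a discussion of sampling properties. The design is a stratified random sample with the bari as primary sampling unit and no village stage, so bari-level estimates carry no sampling design effect. The remark about the smallest sample compares the levels actually sampled, and villages are not among them. All of this stands, and for that reason the sentence should be qualified and not removed.

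Three stronger readings are tempting, and the documents do not support them.

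- A reader might infer that village clustering alone clearly breaks the stated power. With 2717/149 = 18.2 baris per village, SD .64 and village ICCs of .01, .02 and .05, the design effects are 1.17, 1.34 and 1.86, and power for .1 appears to fall to 92%, 88% and 75% (one-sided 1%). But this keeps the adult SD on bari counts. With about 5.3 adults per bari, the figures are 99.9%, 99.2% and 90.5%.
- A reader might take the block figures as the true power. The protocol gives neither a block count nor an ICC, so they show only what is possible.
- A reader might infer that programme effects will be tested with standard errors that are too small. This document does not fix that analysis; it refers applications to the individual project proposals.

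It is also fair to say that this is a multipurpose survey, that the area contrast is introduced only as an example, and that conventional two-sided 5% would leave some slack. None of this makes the figures a worst case for that example. The conservative SD happens to offset village variance, by an amount the protocol does not state, and with few blocks adding baris or adults cannot remove block variance.

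**Conclusion.** The point holds in limited form. The absence of design effects is correct for the sampling of baris and for contrasts that vary within villages. It does not carry over to treatment versus comparison area, so 38%/96% cannot be called a worst case there.

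The size of the loss cannot be determined from the document. If clustering is at village level only, the stated figures remain conservative up to an adult-level ICC of about .035, given about 5.3 adults per bari and rho .25. If variance between blocks matters and blocks are few, power for .1 could be well below 96%: about 48% to 84% under the assumed 6 to 12 blocks and ICC of .005 at two-sided 5%. Confidence is high that the label is wrong for this contrast and low on any single replacement figure.

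**What to change.** - Keep the sentence on design effects, but limit it and the worst-case description to contrasts not assigned by area.
- Restate power for treatment versus comparison area. Give the significance level, the number of blocks, an SD that matches the unit of analysis, and a range of village and block ICCs estimated from surveillance or census data already held.
- State that inference on area-assigned programme effects will use standard errors clustered by village or block.

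The cost is a recomputation, a short text change and probably a less favourable stated power. No extra sample is needed.
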